#### 4.2 Exclusion Criteria

Patients who meet any of the exclusion criteria listed below will not be eligible for participation in the study.

- 1. Anticancer systemic therapy or radiotherapy within 4 weeks or 5 half-lives, whichever is shorter prior to starting the study agents. Prior palliative radiotherapy to metastatic lesion(s) is permitted, provided it has been completed 2 weeks prior to study enrollment, and no clinically significant toxicities are expected (e.g., mucositis, esophagitis).
- 2. Known symptomatic brain metastases requiring steroids. Patients with previously treated diagnosed brain metastases are eligible if they have completed their treatment and have recovered from the acute effects of radiation therapy or surgery prior to study enrollment, have discontinued corticosteroid treatment for these metastases for at least 4 weeks and are neurologically stable.

- 3. Current use of immunosuppressive medication at the time of study enrollment, EXCEPT for the following permitted steroids:
  - a. Intranasal, inhaled, topical steroids, eye drops, or local steroid injection (e.g., intraarticular injection);
  - b. Systemic corticosteroids at physiologic doses ≤10 mg/day of prednisone or equivalent;
  - c. Steroids as premedication for hypersensitivity reactions (e.g. CT scan premedication).
- 4. Subjects who had major surgery within 4 weeks prior to study enrollment.
- 5. Known prior severe hypersensitivity to investigational products or any component in their formulations, including known severe hypersensitivity reactions to monoclonal antibodies (NCI CTCAE v5 Grade ≥ 3).
- 6. Active infection requiring systemic therapy.
- 7. Known history of immune-mediated colitis, inflammatory bowel disease, pneumonitis, and pulmonary fibrosis.
- 8. Subjects with radiographic evidence of pneumonitis on baseline imaging.
- 9. Active or prior autoimmune disease that may deteriorate when receiving an immunostimulatory agent. Patients with type I diabetes, vitiligo, psoriasis, or hyporthyroid disease not requiring immunosuppressive treatment are eligible.
- 10. Prior organ transplantation including allogenic stem cell transplantation.
- 11. Diagnosis of Myelodysplastic Syndrome (MDS).
- 12. Vaccination within 4 weeks of study enrollment and while on trial is prohibited except for the administration of inactivated vaccines.
- 13. Clinically significant (i.e., active) cardiovascular disease: cerebral vascular accident/stroke (< 6 month prior to enrollment), myocardial infarction (< 6 months prior to enrollment), unstable angina, congestive heart failure (≥ New York Heart Association Classification Class II) or a serious cardiac arrhythmia requiring medication.
- 14. Other acute or chronic medical or psychiatric conditions including but not limited to recent (within the past year) or active suicidal ideation or behavior or laboratory abnormality that may increase the risk associated with study participation or investigational product administration or may interfere with the interpretation of study results, and in the judgement of the Investigator, would make the patient inappropriate for entry into this study.
- 15. Pregnant female patients, breastfeeding female patients, fertile male patients, and female patients of childbearing potential who are unwilling or unable to use 2 highly

- effective methods of contraception as outlined in this protocol for the duration of the study, and for at least 6 months after the last dose of study drug administration.
- 16. Hepatitis B virus (HBV) or hepatitis C virus (HCV) infection at screening (positive HBV surface antigen or HCV RNA if anti-HCV antibody screening test is positive).
- 17. Known additional malignancy that is active and/or progressive requiring treatment; exceptions include basal cell or squamous cell skin cancer, in situ bladder cancer, or other cancer for which the patient has been disease-free for ≥ 2 years.
- 18. Persisting toxicity related to prior therapy (NCI CTCAE v5 Grade > 1); however, alopecia and sensory neuropathy Grade ≤ 2, or other Grade ≤ 2 AEs not constituting a safety risk, based on the Investigator's judgement, are acceptable.
- 19. Subjects receiving treatment with strong inhibitors or inducers of CYP3A4 that cannot be discontinued before start of investigational treatment and for the duration of study.
- 20. Subjects with ongoing toxicity (any grade) and/or resolved ICI toxicity (grade 3 or higher only.

#### **5. STUDY TREATMENTS**

The trial regimen will be administered in 28-day cycles. The investigational products to be administered in this trial are: M6620 and avelumab. For both dose escalation and expansion, treatment will continue until disease progression, unacceptable toxicity, and/or withdrawal of patient consent.

### **5.1 Allocation to Treatment**

Eligible patients will be enrolled to receive one of the study drug combinations in an open-labeled, unblinded manner. Patients will be registered and successively assigned to the next available treatment slot at a dose level decided on after the safety evaluation and ongoing observations of earlier enrolled patients. Dose level allocation will be performed after patients have given their written informed consent and have completed the necessary baseline assessments.

# **5.2 Investigational Product Supplies**

M6620 and avelumab will be supplied for the study by EMD Serono. The Investigational Pharmacy will receive a supply of study drug(s) prior to activation with instructions on how to confirm drug receipt. Resupplies will be made during the course of the study based on need.

### 5.2.1 Formulation and Packaging

Packaging and labeling for all study drugs will be in accordance with applicable local regulatory requirements and applicable Good Manufacturing Practice (GMP) guidelines. The information on each study drug will be in accordance with approved submission documents.

### 5.2.1.1 M6620

M6620 drug product will be supplied as a 20 mg/mL solution for injection, in 10 mL clear vials in cardboard boxes with foam inserts, designed for single-use only. M6620 drug product is intended for intravenous administration, only after dilution with 5% dextrose solution in water (D5W).

#### 5.2.1. 2 Avelumab

Avelumab is formulated as a 20.0 mg/mL solution and is supplied by EMD Serono in single-use glass vials, stoppered with a rubber septum and sealed with an aluminum flip-off seal. Each vial will be packaged and labeled per all applicable regulatory requirements and Good Manufacturing Practice Guidelines.

Avelumab will be packed in boxes each containing 8 vials.

Avelumab will be supplied by EMD Serono and packaged, labeled, and distributed for clinical studies by a suitable service provider and finally released by an EMD Serono qualified person under Good Manufacturing Practice conditions. Avelumab will be shipped and must be stored under refrigerated conditions (2°C to 8°C) that are monitored with temperature control monitoring devices.

# 5.2.2 Preparation and Dispensing

#### 5.2.2.1 M6620

M6620 solution for injection must be diluted with 5% dextrose in water solution prior to administration. Do not use 0.9% Sodium Chloride due to incompatibility with M6620. To prepare the infusion solution add the dose volume of M6620 to a non-polyvinyl chloride (non-PVC), di(2-ethylhexyl) phthalate (DEHP)-free EVA infusion bag containing 5% dextrose in water. Gently invert the IV bag 5-10 times to mix the solution. Confirm the solution is clear and free of precipitates and/or particulates. The final concentration must be between 0.075 mg/mL to 1 mg/mL. Place the IV bag into an opaque cover to protect from light.

# **5.2.2.2 Avelumab**

Investigational products should be prepared and dispensed by an appropriately qualified and experienced member of the study staff (e.g. physician, nurse, physician's assistant, nurse practitioner, or pharmacist) as allowed by local, state, and institutional guidance.

Each single-use vial contains 200mg of Avelumab as a preservative-free acetate-buffered solution (pH 5.2) containing mannitol, and polysorbate 20 (Tween 20). For administration, avelumab drug concentrate must be diluted with 0.9% saline solution (sodium chloride for injection) supplied in an infusion bag; alternatively, a 0.45% saline solution can be used if needed. Detailed information

on infusion bags and medical devices to be used for the preparation of the dilutions and subsequent administration will be provided in the Investigational Product Manual.

Any unused portion of the avelumab solution should be discarded in biohazard waste disposal with final disposal by accepted local and national standards of incineration.

### 5.2.3 Administration, Pre-medications, and Infusion Reactions

#### 5.2.3.1 M6620

All doses of M6620 will be administered at the investigator site by well-trained medical staff. The start and stop times of the M6620 infusion, along with the total dose and volume administered, will be recorded in the patients' medical records. Additionally, the start and stop times of any interruptions to infusions and/or changes in rate of M6620 infusion will also need to be recorded in the patients' medical records. The vials of M6620 that are assigned and prepared for patients will be recorded in the pharmacy records. These records will all be available for MDA IND Office representatives to verify compliance.

To minimize the possibility of phlebitis, M6620 should be administered through a large bore catheter into a large caliber peripheral vein. The IV infusion site should be monitored closely for the development of erythema, induration, purulence, tenderness, or warmth.

If any participant develops phlebitis, or signs or symptoms of inflammation that may progress to phlebitis or that the participant cannot tolerate, standard measures should be employed to ameliorate these symptoms (including removal of the infusion catheter and resumption of infusion through a different vein). If standard procedures to limit symptoms of injection site reaction, or pruritus or acute hypersensitivity are insufficient, then the infusion time may be extended beyond 60 minutes, but no more than 90 minutes.

If a patient remains on therapy after 6 months, then treating physician/investigator may consider changing M6620 dosing from every week to every 2 weeks for ease of schedule for the patient. The physician/investigator will maintain the same dose of M6620 when changing from every week to every 2 weeks scheduling. This option will be discussed with every patient remaining on therapy after 6 months, and the decision will be at the discretion of the patient and investigator.

#### **5.2.3.2** Avelumab

All doses of avelumab will be administered at the investigator site by well-trained medical staff. The start and stop times of the avelumab infusion, along with the total dose and volume administered, will be recorded in the patients' medical records. Additionally, the start and stop times of any interruptions to infusions and/or changes in rate of avelumab infusion will also need to be recorded in the patients' medical records. The vials of avelumab that are assigned and prepared for patients will be recorded in the pharmacy records.

Avelumab will be administered as a 1-hour infusion dose of 800 mg administered IV once every 2 weeks.

As a routine precaution, participants enrolled in this study must be observed for 1-hour post infusion for the first 4 infusions, in an area with resuscitation equipment and emergency agents. At all times during avelumab treatment, immediate emergency treatment of an infusion-related reaction or a severe hypersensitivity reaction according to institutional standards must be

assured. In order to treat possible hypersensitivity reactions, for instance, dexamethasone 10 mg and epinephrine in a 1:1000 dilution or equivalents should always be available along with equipment for assisted ventilation.

The treatment recommendations for infusion-related reactions are outlined in **Adverse Drug Reactions Requiring Avelumab Treatment Discontinuation or Modifications** (Section 5.2.5.3.2).

Investigators should also monitor participants closely for potential irAEs, which may become manifest at any time during treatment. Such events include but are not limited to pneumonitis, hepatitis, colitis, endocrinopathies (hypothyroidism, hyperthyroidism, adrenal insufficiency, and type 1 diabetes mellitus), myocarditis, myositis, and rash. See Adverse Drug Reactions Requiring Avelumab Treatment Discontinuation or Modifications details on the management of irAEs. Investigators should also monitor participants closely for potential irAEs, which may become manifest earliest after weeks of treatment. Such events may consist of persistent rash, diarrhea and colitis, autoimmune hepatitis, arthritis, glomerulonephritis, cardiomyopathy, or uveitis and other inflammatory eye conditions. The spectrum of hypothetical irAEs also includes formation of auto antibodies like anti-nuclear antibodies or anti-neutrophil cytoplasmic antibodies. See Adverse Drug Reactions Requiring Avelumab Treatment Discontinuation or Modifications (Section 5.2.5.3.2) for details on the management of irAEs.

If a hypersensitivity reaction occurs, the participant must be treated according to the best available medical practice. Participants should be instructed to report any delayed reactions to the Investigator immediately.

#### 5.2.3.3 Pre-medications

For avelumab, premedication with an antihistamine (for example, 25 to 50 mg diphenhydramine) and with paracetamol (acetaminophen; 500 to 650 mg) IV or oral equivalent approximately 30 to 60 minutes prior to the first 4 doses of avelumab is mandatory, and thereafter is based upon clinical judgment and presence/severity of prior infusion reactions. Standard prophylactic premedication with corticosteroids is not recommended; however, prophylactic steroids to prevent recurrence of infusion-related reaction are not prohibited, based on the Investigator's clinical judgment. Premedication should be administered for subsequent avelumab doses based upon clinical judgment and presence/severity of prior infusion reactions.

Premedication with a corticosteroid and/or an antihistamine should be given to participants who have developed acute hypersensitivity and/or pruritus with M6620 infusion and who continue to receive treatment with M6620.

### 5.2.3.4 Administration of Avelumab and M6620 on the same day

On days when both avelumab and M6620 are to be administered (e.g., C1D1, C1D15), avelumab infusion will precede infusion of M6620, with at least 1 hour in between infusions to observe patients for infusion-related reactions.

# 5.2.3.5 Food Requirements

The investigational products may be administered without regard to food.

# **5.2.4 Patient Compliance**

The information related to each trial drug administration, including the date, time, and dose of study drug, will be recorded in the CRF. The investigator will make sure that the information entered into the CRF regarding drug administration is accurate for each patient. Any reason for non-compliance should be documented.

#### 5.2.5 Recommended Dose Modifications

Every effort should be made to administer the study drugs on the planned dose and schedule.

In the event of significant toxicity, dosing may be delayed and/or reduced as described below. Toxicity will be graded according to NCI CTCAE, version 5.0. In the event of multiple toxicities, dose modification should be based on the worst toxicity observed. Patients are to be instructed to notify Investigators at the first occurrence of any adverse symptom.

Dose modifications may occur:

- Within a cycle: dosing interruption until adequate recovery and dosing reduction, if required, during a given treatment cycle.
- Between cycles: next cycle administration may be delayed due to persisting toxicity when a new cycle is due to start.

#### **5.2.5.1 Dose Interruptions**

Appropriate follow up assessments should be done until adequate recovery occurs as assessed by the Investigator. Criteria required before treatment can resume are described in Dose Delays (Section 5.2.5.2).

Doses may be held as needed until toxicity resolution. Depending on when the AE resolved, a treatment interruption may lead to the patient missing all subsequent planned doses within that same cycle or even to delay the initiation of the subsequent cycle.

If the AE that led to the treatment interruption recovers within the same cycle, then re-dosing in that cycle is allowed. Doses omitted for toxicity are not replaced within the same cycle. The need for a dose reduction at the time of treatment resumption should be based on the criteria defined in Dose Modifications (Section 5.2.5.3), unless expressly agreed otherwise following discussion between the Investigator and the SMC.

In the event of a treatment interruption for reasons other than treatment-related toxicity (e.g. elective surgery) lasting >28 days, treatment resumption will be decided in consultation with the SMC.

#### 5.2.5.2 Dose Delays

Patients experiencing Grade 3 or 4 potentially treatment related toxicity or intolerable Grade 2 toxicity despite supportive care should have their treatment interrupted/delayed. Appropriate follow-up assessments should be done until adequate recovery (or until deemed irreversible) occurs as assessed by the Investigator. A treatment delay of more than 4 weeks due to lack of recovery will result in discontinuation of the patient from the treatment, unless continuation (with dose reduction) upon subsequent recovery is considered in the patient's best interest by the investigator (e.g. proven clinical benefit).

A new cycle of treatment may begin only if:

- a. ANC ≥ 1000/µL
- b. Platelet count ≥ 100,000/µL
- c. Hemoglobin ≥ 8.5 g/dL
- d. Non-hematologic toxicities have returned to baseline or Grade ≤ 1 severity (or, at the investigator discretion, Grade ≤ 2 if not considered a safety risk for the patient).

Withhold scheduled dose for liver function test related AEs (including asymptomatic) Grade  $\geq 3$  until return to baseline or Grade  $\leq 1$  severity. In cases of potential liver injury, consultation with a hepatologist should be considered in the decision to initiate treatment with anti-inflammatory medications.

If these conditions are not met, treatment must be delayed by 1 week. If, after a 1-week delay, all toxicities have recovered within the limits described above, treatment with study drugs, can be resumed. Both study drugs should be delayed simultaneously if applicable. If the patient has not recovered after 1 week of delay, treatment may be delayed by 1 more week. However, initiation of the next cycle can only be delayed by a maximum of 4 weeks (28 days). Therefore, if persisting toxicity does not allow for the resumption of treatment, the patient will be permanently discontinued.

For all ≥ Grade 3 hematological or non-hematological AEs that are NOT study drug-related, after consultation with the Medical Monitor and at the discretion of the treating physician, study drug dosing may be continued.

Elevation of amylase and/or lipase without clinical and/or radiographic evidence of pancreatitis are not considered DLT, and the patient can resume treatment at any grade at the discretion of the treating physician in consultation with the PI.

Patients continuing on protocol after more than a 28 days delay in treatment can continue on a case by case basis after discussion with the Medical Monitor and at the discretion of the treating physician.

Each dose modification or treatment delay has to be documented in the eCRF, including the respective reason.

### 5.2.5.3 Dose Modifications

In the event that a DLT that is at least possibly related to one of the study drugs occurs, patients will halt treatment with study drugs until symptoms resolve to the grade outlined in Section 5.2.5.2, and then treatment can be restarted. After the first two cycles reduction in the frequency of dosing in study drug(s) may be required based on the worst toxicity experienced in the previous cycle.

No specific dose adjustments are recommended for Grade 1/2 treatment-related toxicity. However, investigators should always manage their patients according to their medical judgment based on the particular clinical circumstances.

During the dose escalation arm for the combination of M6620 and avelumab, patients experiencing recurrent and intolerable Grade 2 toxicity may resume dosing at the next lower dose level or at a decreased frequency once recovery to  $\leq$  Grade 1 or baseline is achieved. Patients enrolled in the expansion arms may resume dosing, once recovery to  $\leq$  Grade 1 or baseline is achieved after experiencing recurrent and intolerable  $\geq$  Grade 2. If a dose or frequency reduction is required due to the treatment related toxicity, this may be allowed as an alternative to discontinuation of treatment, upon agreement with the MDACC IND Office.

Once a patient has a dose reduction or reduction in the frequency in the dosing for a drug-related toxicity, the dose will not be re-escalated. Patient requiring more than two dose reductions will be withdrawn from treatment unless otherwise agreed between the investigator and the MDACC IND Office.

Adverse events (both non-serious and serious) associated with study drug(s) exposure may represent an immunologic etiology. These adverse events may occur shortly after the first dose or several months after the last dose of treatment. The immunotherapy drug avelumab must be withheld for drug-related toxicities and severe or life threatening AEs as per Table 3. Where appropriate, these guidelines include the use of oral or intravenous treatment with corticosteroids as well as additional anti-inflammatory agents if symptoms do not improve with administration of corticosteroids. Note that several courses of steroid tapering may be necessary as symptoms may worsen when the steroid dose is decreased. The dose modification guidelines are intended to be applied when the physician determines the events to be related to avelumab.

For subjects whose dose was withheld due to toxicity, subjects may resume immunotherapy study drug (avelumab) upon resolution of toxicity to Grade 0-1 or baseline.

Note: The general treatment recommendations outlined in Sections  $\underline{5.2.5.1}$ ,  $\underline{5.2.5.2}$ , and  $\underline{5.2.5.3}$  can be used **unless** more specific treatment guidelines are outlined in Sections  $\underline{5.2.5.3.2.1}$  and  $\underline{5.2.5.3.2.2}$  below.

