- 1. Isolated Grade 4 lymphopenia without clinical correlate.
- 2. Any Grade 4 neutropenia < 7 days duration not associated with any clinical symptoms.
- 3. Other single laboratory values out of normal range that have no clinical correlate, and resolve to Grade ≤ 1 or to baseline within 7 days with adequate medical management.
- 4. Any Grade 3 autoimmune thyroid-related toxicity that clinical resolves to Grade ≤ 2 within 7 days of initiating therapy.
- 5. Grade 3 diarrhea persisting < 72 hours after initiation of medical management.
- 6. Grade 3 non-recurrent skin toxicity that resolves to Grade ≤ 1 in < 7 days after initiation of medical management.
- 7. Transient Grade 3 fatigue, local reactions, flu-like symptoms, fever, headache, nausea, and emesis that resolve to Grade ≤ 1 in < 48 hours after initiation of medical management.
- 8. Tumor flare phenomenon defined as local pain, irritation, or rash localized at sites of known or suspected tumor that resolve to Grade ≤ 2 within 6 days.
- 9. Grade 3 infusion-related reaction resolving within 6 hours from the end of infusion and controlled with medical management.

Elevation of amylase and/or lipase without clinical and/or radiographic evidence of pancreatitis are not considered DLTs, and the patient may resume treatment at any grade at the discretion of the treating physician in consultation with the PI.

During dose escalation, patients who receive <75% of the planned dose of the investigational products in the combination during Cycle 1 for reasons unrelated to study drug(s) are not evaluable for DLT and will be replaced.

In rare instances, an event may fall within the definition of a DLT as defined above but the event may not be considered a DLT (e.g. not clinically meaningful or significant). If this occurs, the PI will thoroughly review the event and supporting data, and the reasons for not considering the event a DLT will be clearly documented with supporting rationale. In addition, other events may occur that do not meet the definition of a DLT but are concerning to the PI, may then be considered to be DLTs.

In the event that a DLT is at least possibly related to the study drug(s), patients will halt treatment with the study drug(s) until symptoms resolve to the grade outlined in Section 5.2.5.2. Study drug(s) may be restarted as described in Section 5.2.5.

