## 5.2.5.3.1 Adverse Drug Reactions Requiring M6620 Treatment Discontinuation or Modifications

In the case of occurrence of an AE attributed to M6620, treatment may be interrupted and may resume when all toxicities have returned to Grade 2 or less, at the discretion of the Investigator. Except for participants in Part A during the DLT observation period, doses of M6620 may be reduced after occurrence of a related AE using the following guidelines, any exceptions to this dose modification criterion will need to be agreed between the PI and IND Office:

- a. For Grade 4 hematologic toxicity: the dose of M6620 will be reduced by 25%.
- b. For Grade 3 non-hematologic toxicity: M6620 will be discontinued.
- c. For Grade 4 non-hematologic toxicity: M6620 will be discontinued.

Guidelines for dose modification for toxicity are provided below. The final dose reduction or delay for each participant may be determined by the Investigator. However, these guidelines provide the minimum dose reduction or delay criteria. Additionally, if a participant who is responding to treatment experiences toxicity even after 2 dose reductions, the participant may continue to receive treatment if in the judgment of the Investigator it is in the best interest of the participant. In this case the dose of M6620 will further be reduced by at least 25%.

In case of M6620 Grade 3 or higher toxicity (excluding fatigue or nausea/vomiting/diarrhea adequately managed by supportive care), treatment will be interrupted and may be resumed when all toxicities have returned to Grade 2 or lower, at the discretion of the Investigator.

For the following hematologic toxicities, once the toxicity has returned to Grade 2 or lower, dosing can be resumed with 1 dose level reduction. If, after 1 dose level reduction, any of the below drug-related hematologic toxicities are subsequently observed, then dosing may be resumed with 2 dose level reductions:

- a. Grade 4 thrombocytopenia;
- Febrile neutropenia (growth factor support, per site protocol, may be used in lieu of dose reduction) except during the DLT assessment period prior to occurrence of a DLT. Once a DLT has occurred, it is acceptable to use growth factor support even during the DLT period;
- c. Grade 4 neutropenia lasting more than 7 days.

If any of the drug-related toxicity listed below is subsequently observed, the M6620 dose will be reduced by 1 dose level:

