# 9.1.2 DLT Analysis Set

The DLT analysis set is a subset of the safety analysis set and includes all enrolled patients in the dose escalation phase, receive at least one dose of the combination treatment, and either experience DLT during the first cycle (28 days) of treatment, or complete the DLT observation period for the first cycle of treatment.

Patients without DLTs who withdraw from study treatment before receiving at least 75% of the planned dose of each of the investigational products in the combination in Cycle 1 for reasons other than toxicity, which are attributable to the investigational products are not evaluable for DLT. Additional patients will be enrolled in the specific cohort to replace patients who are not considered DLT evaluable.

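### The rules on reducing dose or frequency inside the 28-day DLT window conflict, and a patient reduced in Cycle 1 for related toxicity can count as DLT-free at the assigned level

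*Combined protocol and SAP*

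**What the plan says.** Section 5.2.5.3 (Dose Modifications) states that in the escalation phase "patients experiencing recurrent and intolerable Grade 2 toxicity may resume dosing at the next lower dose level or at a decreased frequency", once the toxicity has recovered to Grade 1 or baseline. It names no cycle. The same section says "No specific dose adjustments are recommended for Grade 1/2 treatment-related toxicity", that a reduction for related toxicity is one where "this may be allowed as an alternative to discontinuation of treatment, upon agreement with the MDACC IND Office", and that after a reduction "the dose will not be re-escalated".

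Section 5.2.5.3.1, on M6620, reads: "Except for participants in Part A during the DLT observation period, doses of M6620 may be reduced after occurrence of a related AE". The protocol otherwise speaks of Arm A, which covers escalation and expansion, and of the dose escalation phase. Part A appears only here. The note closing 5.2.5.3 lets specific guidance override the general rules, but it names only the two avelumab subsections, 5.2.5.3.2.1 and 5.2.5.3.2.2.

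On who counts for DLT, section 3.3 says that patients below 75% of planned Cycle 1 dose "for reasons unrelated to study drug(s) are not evaluable for DLT and will be replaced". Section 9.1.2 includes a patient who has a DLT "or complete the DLT observation period for the first cycle of treatment", and removes only DLT-free patients who withdraw before 75% of planned dose for reasons other than toxicity. Section 3.5 puts all enrolled participants into the DLT analysis. Under section 3.4 the MTD is the highest level with fewer than 2 patients with DLT among at least 6.

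**The concern.** Establishing the MTD and recommended phase 2 dose is a primary objective. A dose level is judged on the DLT count in three to six patients over 28 days, which presumes that those patients were treated at that level. One passage allows a drop in dose or frequency for toxicity during that window. Another forbids the dose drop for a group that cannot be identified. No analysis rule requires a patient to have stayed at the assigned level. A patient who did not tolerate the level well enough to stay on it could then be recorded as evidence that the level is tolerated. When escalation is decided on the first three patients, one such patient is a third of the evidence. A cleared level also becomes available for intra-patient escalation (section 3.2.1).

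**Working it through.** **1. Does any text settle Cycle 1?**
- Section 5.2.5.3 permits a lower level or lower frequency in escalation, with no time limit.
- Section 5.2.5.3.1 bars M6620 dose reduction in the DLT window for Part A. If Part A means escalation, or all of Arm A, this forbids the dose drop that 5.2.5.3 permits. If it means something else, escalation has no bar. On its wording the bar covers dose and is silent on frequency.
- The precedence note does not name 5.2.5.3.1.
- The sentence "After the first two cycles reduction in the frequency of dosing in study drug(s) may be required" says when a frequency change may become necessary. It prohibits nothing earlier and does not mention dose level.

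**2. What would the patient receive?** M6620 is given on Days 1, 8, 15 and 22 (Study Calendar, footnote 16). Omitted doses are not made up within the cycle (5.2.5.1). I assume that recurrence can be seen only after a second dose, so Day 15 is the earliest reduced visit. Fraction received = sum of doses given / (4 × assigned dose).

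| Cycle 1 pattern, level 2 (mg/m²) | Received / planned | Fraction |
|---|---|---|
| One level lower from Day 22: 480, 480, 480, 240 | 1680 / 1920 | 87.5% |
| One level lower from Day 15: 480, 480, 240, 240 | 1440 / 1920 | 75.0% |
| Day 15 held, Day 22 one level lower: 480, 480, 0, 240 | 1200 / 1920 | 62.5% |
| Every two weeks after Day 8, dose unchanged: 480, 480, 0, 480 | 1440 / 1920 | 75.0% |

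The fractions at level 1 (240 to 120, planned 960) are the same: 840, 720, 600 and 720 mg/m².

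**3. Is the patient removed from the DLT set?**
- At 75.0% the below-75% rule in 3.3 is not met, whatever the reason.
- At 62.5% it is still not met, because the reason is related to study drug.
- The exclusion in 9.1.2 needs withdrawal, and for a reason other than toxicity.
- The general DLT threshold in 3.3 is Grade 3 or higher non-hematologic, or Grade 4 or higher hematologic, so Grade 2 toxicity does not meet it.

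The patient completes the window and counts as DLT-free at the assigned level, absent a discretionary DLT call.

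**4. How much could it matter?** The documents give no DLT risk for escalation and no effect of early reduction, so this is an illustration under assumptions. Let p be the Cycle 1 DLT risk at full dose, and suppose that m of 6 patients are reduced and have risk p/2. Then

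P(at most 1 DLT in 6) = (1−p)^(6−m) × (1−p/2)^m × [1 + (6−m)·p/(1−p) + m·(p/2)/(1−p/2)].

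For p = 0.4, m = 1: 0.6^5 × 0.8 × [1 + 5 × 0.6667 + 0.25] = 0.0622 × 4.583 = 0.285.

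| Full-dose risk p | m = 0 | m = 1 | m = 2 |
|---|---|---|---|
| 0.2 | 0.655 | 0.696 | 0.737 |
| 0.3 | 0.420 | 0.474 | 0.532 |
| 0.4 | 0.233 | 0.285 | 0.346 |

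Under these assumptions each reduced patient adds about 4 to 6 percentage points to the chance of meeting the MTD criterion. Halving the whole-cycle risk is generous, since the first two doses were full. Against that, the model treats reduced patients as having average risk, although they have already shown recurrent toxicity. A reduction that averts no DLT leaves the count unchanged; one that averts a DLT favors clearing the level.

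**The case against.** The strongest reply is that the bar exists. M6620 is the only drug whose dose differs between levels, the DLT window belongs mainly to escalation, and a drug-specific limit can be read alongside a general permission. On that reading Part A means escalation and no dose-level drop occurs in Cycle 1. This is a reasonable guess at the intent, but it rests on an undefined term, and the precedence note passes over 5.2.5.3.1. It also leaves a frequency reduction unaddressed.

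The safeguards are real. The third listed DLT in section 3.3 lets the SMC class a related event as a DLT with no grade floor. The principal investigator may also do so for concerning events. The SMC must approve a dose-level summary before any level change (3.5), a reduction needs IND Office agreement, and each modification is recorded in the eCRF with its reason (5.2.5.2). A reduced patient is therefore unlikely to go unnoticed. What remains is that none of these safeguards sets a criterion for dose received or says how the patient is counted.

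Some stronger readings are tempting, and the documents do not support them:
- **A level could be cleared by patients who never received it.** Such a patient has full doses on at least Days 1 and 8 and misses only part of the assigned dose.
- **Any Grade 2 event opens the door.** The trigger is toxicity that is both recurrent and intolerable, with recovery before dosing resumes.
- **Cycle 1 exposure could fall to 62.5% by lowering the level after one dose, or to 50% by two-weekly dosing from the start.** Both need a change before a second dose could show recurrence.
- **The reference to the first two cycles is a third conflicting rule.** It bars nothing earlier.
- **The expansion toxicity boundaries in 9.6 are affected.** A Cycle 1 DLT that prompts reduction is already counted there, and no effect on 5/10 or 8/20 has been shown.

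**Conclusion.** The point holds as a conflict between passages combined with a gap in the DLT counting rules. Following 5.2.5.3 as written in Cycle 1, a patient with recurrent and intolerable Grade 2 toxicity can receive 75.0% of planned M6620, or 62.5% with a held Day 15, and still count as DLT-free at the assigned level unless discretion is used. The direction of any bias is toward clearing the level. Its size cannot be established from the documents; the 4 to 6 points per reduced patient rest on assumed full-dose risks of 20% to 40% and an assumed halving of risk. How often such reductions would happen is also unknown. Because a primary objective depends on this count, the passages should be reconciled, even though the existing oversight makes a serious error less likely.

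**What to change.** 1. Reconcile 5.2.5.3, its precedence note and 5.2.5.3.1 so that one stated rule governs both dose and frequency reduction inside the 28-day DLT window, and replace Part A with the phase or phases meant. Which clinical rule applies is for the sponsor and investigators to decide; none is proposed here.
2. If any Cycle 1 reduction remains possible, state in 9.1.2 and 3.5 one explicit way in which a patient reduced for related toxicity enters the DLT count: for example counted as a DLT, replaced, or kept in the denominator and reported separately. The choice should be fixed before escalation data are reviewed.
3. List these patients, with percent of planned dose of each drug received in Cycle 1, in the dose-level summary that already goes to the SMC.

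The cost is a wording amendment and one added line in an existing report. The eCRF already captures each modification and its reason. If replacement is chosen, a level may occasionally need an extra patient.
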